Low vs Standard Dose Indocyanine Green in the Identification of Biliary Anatomy Using Near-Infrared Fluorescence Imaging: A Multicenter Randomized Controlled Trial

NCT04942665

12/9/2021

1. Title:

- Low dose ICG for near-infrared fluorescence imaging of biliary tract

2. Investigators:

- [name], PhD (PI)
- [name] (co-PI, PI proxy)
- [name] (co-Investigator)
- [name] (co-Investigator, medical student)
- [name] (Study Coordinator)

3. Abstract:

We have a series of surgical cases in which we have been able to achieve excellent intraoperative biliary visualization with a greatly decreased (50-200X fold lower) dose of ICG than the previously published dose. Furthermore, this decreased dose was visible in about 15-20 minutes from the time of injection with low liver background fluorescence, a significant improvement that would make its utilization in the operating room more practical. We hypothesize that a lower dose will allow adequate visualization of the extrahepatic biliary tree, including the cystic, common hepatic, and common bile ducts. Confirmation of this hypothesis would mean that a lower dose of ICG can be administered on the same day of surgery in order to augment real-time intraoperative localization of the extrahepatic biliary tree, thereby providing a safe, feasible, and cost-effective strategy for the surgical treatment of liver disease.

We intend to test our hypothesis with the following specific aims:

Aim: To compare the efficacy and utility of a low dose ICG (0.05 mg) protocol with a previously published dose (2.5 mg) in imaging the extrahepatic biliary tract.

4. Background:

Near-infrared fluorescence (NIRF) imaging after an intravenous injection of indocyanine green (ICG) allows for the intraoperative identification of biliary anatomy. ICG binds to plasma proteins and emits light with a peak wavelength around 830nm when illuminated with near-infrared light. ICG is exclusively excreted by the liver, and biliary excretion lasts from several minutes to 24 hours post-injection (1). NIRF imaging has been shown to be a safe, easy, fast, cost-effective strategy for delineating biliary anatomy because it decreases the risk of bile duct injury and does not require radiation (2)(3)(4). Research from our group, among others, has shown that visualization of the extrahepatic biliary tract is adequate at a dose on the order of 2.5 mg administered at least 15 minutes prior to visualization (5).

Since the advent of NIRF, imaging technology has improved, with increasing sensitivity and improved intraoperative displays. Whether these improvements have resulted in increased sensitivity and utility has not yet been demonstrated, nor has the possibility of whether improved technology has decreased either the dose required for adequate visualization or the time interval prior to optimal visualization.

5. Specific Aim:

To compare the efficacy and utility of a low dose ICG (0.05 mg) protocol with a previously published dose (2.5 mg) in imaging the extrahepatic biliary tract.

6. Research Plan:

Current standard of care for this service is to administer 2.5 mg of ICG preoperatively to patients before surgical bile duct visualization. If there is any further need for anatomic information, then a combination of ultrasound and X-ray cholangiography is used. For this study, adult patients scheduled to undergo a laparoscopic hepatic or biliary operation will be randomized to two groups 1) low dose (0.05 mg) or 2) standard dose (2.5 mg) of ICG preoperatively on the day of surgery. Patients with a history of adverse reactions or known allergy to ICG, iodine, or iodine dyes will be excluded. Pregnant and/or lactating patients will also be excluded. Participants will receive a baseline assessment. Demographic information, including age, gender, ethnicity or race, body mass index, American Society of Anesthesiologists class, preoperative diagnosis, liver function, and complete medical history, will be collected. Case difficulty will be graded by the primary surgeon based on standardized criteria (<https://pubmed.ncbi.nlm.nih.gov/29956029/>). The PINPOINT Endoscopic Fluorescence Imaging System (Stryker Corporation, Kalamazoo, Michigan) will be used. This device enables the surgeon to simultaneously see real-time, high-definition visible-range and NIR fluorescence videos and to superimpose them. It is currently approved by the FDA for intraoperative near-infrared fluorescence imaging. Essentially, it is a standard laparoscopic device with an added excitation laser at 805 nm and a filter set to allow for visualization of ICG fluorescence. The visualization of the biliary tree will be recorded.

Low dose or standard dose ICG will be administered by the anesthesiologist as guided by the study coordinator at the beginning of the case. The operating surgeon will be blinded to the dose given. At two points during the operation (1- prior to the

[figure not shown]

Figure 1. Representative examples of intraoperative images of biliary tract. GB, gallbladder; L, liver; CHD, common hepatic duct; Cys, cystic duct. (Zarrinpar et al, *Surgical Innovation* 2016)

dissection of the biliary tract and 2- upon completion of the dissection and establishment of the critical view of safety), a *qualitative assessment* will be made by the primary surgeon based on the quality of the intraoperative visualization of the extrahepatic biliary tree (being able to identify and distinguish the common bile duct, the common hepatic duct, and the cystic duct from the surrounding structures and from each other) on a scale of 1 to 5 (1 = no improvement/identification not confirmed; 2 = marginally improved; 3 = sufficiently improved; 4 = well improved; 5 = greatly improved/exceeds expectations). The recorded visualization will also be assessed by a blinded independent surgeon who will use the same scale. A quantitative assessment will also be performed on the recorded visualization using ImageJ (US National Institutes of Health, Bethesda, MD; <http://imagej.nih.gov/ij/>) by dividing the fluorescence intensity signal of the common bile duct by that of the surrounding fat or liver. These quantitative measurements will allow an independent measure of duct visualization. Both quantitative and qualitative scores will be compared to determine whether there are significant differences between the doses. A total of thirty patients (15 in each arm) will be required for more than a 90% power to detect a difference in the duct-to-liver ratio of 0.2 between the two groups, given an alpha of 0.05 and a standard deviation of 0.15. These estimates are based on our previously published results. (5)

Patients who are not able to provide informed consent and have a history of sensitivity or allergy to shellfish, ICG, or iodine will be excluded from the study.

Randomization: Identical envelopes will be made with a card marked either standard or low dose to be chosen in blocks of four. At the time of enrollment, an envelope will be selected at random from a box and the subject will be assigned to the corresponding arm. This envelope will then be discarded to allow for equal numbers in each group.

For the purposes of the study, the recorded videos will be stored on a secure local server with access limited only to the study team. This will allow the team to perform the image analysis and related calculations. At the end of the study, the videos will be deidentified and maintained for possible future research.

7. Possible Discomforts and Risks:

Using a lower dose of ICG may lead to poorer visualization of the anatomy during surgery compared to the standard dose. The surgeons, however, routinely use other methods of visualization during surgery (such as ultrasound or x-rays) that would decrease the risks of poor visualization during the operation. The most commonly reported adverse reactions to ICG are typically mild and included pruritus, shortness of breath, and nausea. Less commonly reported events include bronchospasm (a condition wherein muscles lining the airways of the lungs constrict or tighten, reducing airflow), laryngospasm (a spasm of the vocal cords that temporarily makes it difficult to speak or breath), low blood pressure, and cardiac arrest. IVs are routinely used by clinicians and they are considered to be low risk.

8. Possible Benefits:

Decreasing the dose of ICG may lead to better visualization of the anatomy during surgery and also it may decrease the risk of side-effects.

9. Conflict of Interest:

The investigators have no real or potential conflict of interest with regard to this research project.

10. Data Safety and Monitoring Plan

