Low vs Standard Dose Indocyanine Green in the Identification of Biliary Anatomy Using Near-Infrared Fluorescence Imaging: A Multicenter Randomized Controlled Trial

NCT04942665

9/1/2022

Mann-Whitney tests were conducted for the quantitative and qualitative assessments to identify any significant differences between the 2 doses of ICG. A 2-way ANOVA was also conducted to compare the individual fluorescence intensities of the liver, bile duct, and background fat between the 2 doses. A p value of <0.05 was considered statistically significant. All tests were performed using GraphPad Prism software version 9.4.1 (GraphPad Software, San Diego, CA). Power analysis based on results from our previous study indicated that a total of 26 patients (13 in each arm) would be required for 90% power to detect a difference in the primary outcome measure of bile duct-to-liver fluorescence intensity ratio of 0.2 between the 2 groups, given an alpha of 0.05 and a SD of 0.15. We therefore powered the study to allow for accrual of adequate numbers of subjects at each center independently.

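### Liver function is recorded at baseline but left out of the dose comparison, so precision is forgone and chance imbalance goes unaddressed

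*Protocol*

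**What the plan says.** - **Entry.** Protocol section 6: "adult patients scheduled to undergo a laparoscopic hepatic or biliary operation will be randomized to two groups". The exclusions there are allergy or sensitivity, pregnancy or lactation, and inability to consent; for example, "Patients with a history of adverse reactions or known allergy to ICG, iodine, or iodine dyes will be excluded". None concerns liver function.
- **Excretion.** Protocol section 4: "ICG is exclusively excreted by the liver, and biliary excretion lasts from several minutes to 24 hours post-injection".
- **Baseline data.** Protocol section 6 lists variables ending with "preoperative diagnosis, liver function, and complete medical history, will be collected". It does not say which liver tests are meant.
- **Allocation.** Protocol section 6, randomisation paragraph: "Identical envelopes will be made with a card marked either standard or low dose to be chosen in blocks of four". No stratification factor is named.
- **Analysis.** SAP: "Mann-Whitney tests were conducted for the quantitative and qualitative assessments to identify any significant differences between the 2 doses of ICG". It adds a 2-way ANOVA of liver, duct and fat intensities by dose. No patient covariate, stratified test or subgroup appears in either document.
- **Primary outcome and size.** The SAP names the duct-to-liver ratio as primary and gives 13 per arm for 90% power at a difference of 0.2 (SD 0.15, alpha 0.05). Protocol section 6 gives 15 per arm for more than 90%.
- **Wider claim.** The abstract (section 3) says confirmation would provide a "cost-effective strategy for the surgical treatment of liver disease".

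**The concern.** The primary outcome divides duct signal by liver signal. If the dye reaches bile only through the liver, a patient's liver function could plausibly affect both parts of the ratio, apart from any dose effect. Entry is open to hepatic and biliary operations with no liver-function limit, so liver function may vary among those enrolled. Nothing in allocation or analysis takes account of it, although it is recorded.

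Two things are at stake. The first is precision: outcome variation that a baseline measurement could explain stays in the error term. The second is interpretation: with 13 to 15 per arm, the arms can differ by chance in liver function, and the plan gives the reader no adjusted result against which to judge the unadjusted one.

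**Working it through.** **Inputs.** Difference 0.2, SD 0.15, alpha 0.05, and 13 (SAP) or 15 (protocol) per arm. Two-sided testing is assumed because sidedness is not stated. Assumptions not in the documents: the share R² of the ratio's variance explained by one baseline value (10-30%), the share p of patients with altered liver handling, and the shift s in the ratio between such patients and the rest.

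**1. The plan's own figure.** For a two-sample t-test, noncentrality = 0.2 / (0.15 × √(2/n)).
- n = 13: 0.2 / 0.0588 = 3.40 on 24 df, power 90.3%.
- n = 15: 0.2 / 0.0548 = 3.65 on 28 df, power 94.1%.

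Both stated sizes are consistent with their stated power.

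**2. Adjustment on the t-test scale.** Residual SD = 0.15 × √(1 − R²), which is 0.142 at R² = 10% and 0.126 at 30%. Power becomes 93.0% to 97.4% at 13 per arm and 96.0% to 98.8% at 15. Charging one degree of freedom for the covariate changes these by about 0.1 percentage point or less.

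**3. Adjustment on the rank scale.** The planned test is Mann-Whitney, so the fair comparison is with Quade's rank ANCOVA: rank the ratio and the covariate, regress one set of ranks on the other ignoring dose, and compare the residuals between doses. Simulated power (normal data, 20,000 trials per cell):

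| R² | 13 per arm: Mann-Whitney | 13 per arm: rank ANCOVA | 15 per arm: Mann-Whitney | 15 per arm: rank ANCOVA |
|---|---|---|---|---|
| 0 | about 87% | about 87% | about 92% | about 92% |
| 10% | about 87% | about 90% | about 92% | about 94% |
| 30% | about 87% | about 95% | about 92% | about 97% |

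Type I error of the rank ANCOVA was near 5% throughout. The Mann-Whitney figure of 87% sits below 90% because the stated size fits a t-test; that is a separate matter from this point.

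**4. Chance imbalance.** Treat the number of affected patients in each arm as an independent Binomial(n, p) count. At p = 30%, the arms differ by 3 or more in 28% of trials at 13 per arm and 32% at 15. For p from 20% to 50% the ranges are 22-33% and 25-36%. The effect on the arm difference is (3/n) × s:
- s = 0.1, n = 15: 0.2 × 0.1 = 0.02.
- s = 0.2, n = 13: 0.231 × 0.2 = 0.046.
- s = 0.3, n = 13: 0.231 × 0.3 = 0.069.

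That is 10% to 35% of the 0.2 target.

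**5. Subgroups.** At SD 0.15, t-test power for a 0.2 difference within a subgroup is 24% with 3 per arm, 36% with 4 and 55% with 6. At these totals, a split by operation type can only be descriptive.

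**The case against.** The strongest reply is that nothing is wrong. Randomisation makes the unadjusted Mann-Whitney test valid whatever the case mix, and its type I error rate already allows for chance imbalance. A broad entry population is a legitimate choice. All of this stands, so a reader who infers that pooling hepatic and biliary operations biases the dose comparison goes further than the documents allow.

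A reader might also infer that case mix has cost the trial power. That would follow only if 0.15 were the SD among patients with similar livers. For example, with p = 30% and s = 0.2 the total SD would be √(0.15² + 0.3 × 0.7 × 0.2²) = 0.176, and t-test power 79.5% at 13 per arm and 85.3% at 15. The protocol takes its estimates from the group's earlier study and does not describe that study's case mix. If 0.15 already includes a similar mix, the stated power stands and adjustment only adds to it. The figures offered here use that cautious reading.

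Three further objections have force:
- The protocol states only the excretion route. An effect of liver function on the ratio is an inference, and a within-patient ratio may cancel part of it.
- A hepatic operation is not the same as impaired liver function. The useful covariate is a measured liver value, not the operation type.
- The SAP says numbers were set to be adequate at each center separately, so the total may exceed 26 to 30. The gain in power would then be smaller and chance imbalance proportionally less.

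These limit the size of the point. They do not remove it, because the adjustment uses a variable already collected and costs almost nothing if that variable proves uninformative.

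**Conclusion.** The point holds as one of forgone precision and unaddressed chance imbalance. On the assumption that one baseline liver value explains 10-30% of the ratio's variance within the stated SD of 0.15, rank-based power rises by about 3 to 8 percentage points at 13 per arm (87% to 90-95%) and about 2 to 5 at 15 per arm (92% to 94-97%). The documents give no value for R², and at R² = 0 the gain is nil.

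A reader might also take the abstract's liver-disease clause for a planned conclusion that the trial cannot support. It is one sentence of rationale. The aim (section 5) and the SAP's primary outcome concern imaging of the biliary tract, and no liver-disease analysis is planned. The clause is broader than the design and should not be carried into the conclusions, but that is a matter of wording.

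**What to change.** Before unblinding, amend the SAP to:
1. Name one baseline liver-function value that is actually collected (bilirubin, for example) and specify a Quade rank ANCOVA of the duct-to-liver ratio adjusted for it.
2. State which test decides. Either the adjusted test is primary with Mann-Whitney as sensitivity analysis, or Mann-Whitney stays primary with the adjusted test as a prespecified sensitivity analysis.
3. Show the ratio by dose separately for hepatic and biliary operations, as description without tests.
4. Limit the concluding claim to imaging the extrahepatic biliary tract in the mix of patients enrolled.

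The cost is SAP wording and one degree of freedom, with no new patients or data and no change to the stated sample size. The SAP is written in the past tense. If the comparison has already been seen by dose, Mann-Whitney should stay primary and the adjusted result should be labelled post hoc.

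### The 1–5 visualization score is defined as quality but anchored as improvement, and score 1 covers both 'no improvement' and 'not identified', which can blur the dose comparison

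*Protocol*

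**What the plan says.** Protocol section 6 (Research Plan) has the primary surgeon rate each case twice, once before the biliary tract is dissected and once "upon completion of the dissection and establishment of the critical view of safety". The rating is to be "based on the quality of the intraoperative visualization of the extrahepatic biliary tree", which the protocol explains as "being able to identify and distinguish the common bile duct, the common hepatic duct, and the cystic duct from the surrounding structures"; the ducts must also be told apart. The scale then reads "1 = no improvement/identification not confirmed; 2 = marginally improved; 3 = sufficiently improved", followed by "4 = well improved; 5 = greatly improved/exceeds expectations". The protocol adds: "The recorded visualization will also be assessed by a blinded independent surgeon who will use the same scale".

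The same section says that the scores will be compared between doses. The SAP applies Mann-Whitney tests to the qualitative assessments. It does not redefine the scale, say which reading or rater is analyzed, or separate the two meanings of score 1. It names the bile duct-to-liver fluorescence ratio as the primary outcome.

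The hypothesis in section 3 (Abstract) is that the lower dose gives "adequate visualization of the extrahepatic biliary tree, including the cystic, common hepatic, and common bile ducts".

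**The concern.** The introductory wording describes an absolute state: can the three ducts be identified and told apart? The anchors describe a change, but from what is not said. It could be the white-light view, the earlier reading, or what the surgeon is used to. The two constructs agree when fluorescence turns an unclear field into a clear one. They part when the ducts were already clear.

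Score 1 is where this does harm, because it joins two opposite situations: fluorescence added nothing because the anatomy was already plain, and fluorescence failed to show the anatomy. A low score then does not tell the reader which one occurred.

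At stake is the dose comparison on this score. The protocol computes its quantitative ratio from the common bile duct only, divided by fat or liver. The cystic and common hepatic ducts, both named in the hypothesis, are covered by no other planned outcome.

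**Working it through.** **1. The plan's own figure.** The only power calculation concerns the duct-to-liver ratio: difference 0.2, SD 0.15, alpha 0.05 (two-sided assumed). The noncentrality is 0.2 / (0.15 × √(2/n)), which is 3.40 at n = 13 and 3.65 at n = 15 per arm. The noncentral t gives 90.3% power at 13 per arm (SAP states 90%) and 94.1% at 15 per arm (Protocol states more than 90%). Both reproduce, and neither depends on the wording of the scale. No power is stated for the 1–5 score.

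**2. The wording applied to three patients at one reading.**

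| Patient | Following the introductory wording (quality) | Following the anchors (improvement) |
|---|---|---|
| Ducts unclear in white light, clear in fluorescence | high | high |
| Ducts plain in white light, also fluoresce | high | 1 (no improvement) |
| No duct identified | 1 | 1 |

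The second row is the problem. One rater can give a high score and another a 1 to the same patient, each following the text. Under the anchor reading, the second and third rows share a code.

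**3. Timing.** By the second reading the dissection is finished and the critical view is established, so the cystic duct at least should be exposed and fluorescence has less to add. The second row is therefore probably more common at that reading. This is an inference from the timing; the documents do not say it.

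**4. Illustration of size.** The documents give no score distribution and no rate of already-plain ducts, so every input here is assumed. A share f of patients in both arms is reset to 1; 15 per arm; asymptotic Mann-Whitney, two-sided 0.05, by simulation.

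- Pair I, scores 1–5: 5/10/20/35/30% against 25/30/25/15/5%. Mean scores are 3.75 and 2.45, a difference of 1.30.
- Pair II (wider separation): 2/3/10/30/55% against 40/30/20/8/2%. Mean scores are 4.33 and 2.02, a difference of 2.31.

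Resetting a share f to 1 in both arms multiplies the mean difference by (1 − f). At f = 20% the differences become 1.30 × 0.8 = 1.04 and 2.31 × 0.8 = 1.85.

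| f | Power, pair I | Power, pair II |
|---|---|---|
| 0 | about 82% | about 100% |
| 10% | about 64% | about 98% |
| 20% | about 48% | about 89% |

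**5. A model closer to the second row.** Here only well-visualized patients (true score 4–5) are at risk, and a share q of them is coded 1. With assumed distributions 5/10/20/30/35% and 20/30/25/15/10%, power at 15 per arm falls from 69% (q = 0) to 51% (q = 10%) and 39% (q = 20%). At 13 per arm the figures are 62%, 47% and 33%. This recoding falls harder on the arm with better visualization. The share scored 1 in that arm is 0.05 + q × 0.65, against 0.20 + q × 0.25 in the other. At q = 20% this is 18% against 25%; at q = 50% it is 37.5% against 32.5%, so the better arm then has more scores of 1.

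**The case against.** The strongest reply is that the introductory wording governs. A surgeon told to rate quality of visualization would not give 1 to ducts that fluoresce well, so the conflation need not occur. This stands in part: the anchors permit it but do not force it. What remains is that two raters can follow the text and disagree, and nothing in the Protocol or SAP settles which is right.

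A second reply is that improvement is worth measuring. The stated aim includes utility as well as efficacy, and the device shows visible-range and near-infrared video together, so white light is a natural reference. That is fair, and it is a reason to keep an improvement item. It does not justify giving that item and failed identification one code.

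Third, there are partial safeguards. The score is not primary. The first reading precedes dissection. Case difficulty and body mass index are collected, and videos are kept. Difficulty and body mass index may help to interpret a 1, but they do not record whether each duct was visible without fluorescence. The recordings are more useful, and the fix relies on them.

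Fourth, the power figures rest wholly on assumption. This stands in full. At f = 5% pair I still gives 72–74%, and pair II loses little even at 20%.

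A reader might go further and infer that the qualitative outcome cannot show whether a dose worked, or that every patient with plain ducts scores 1. The documents do not support either. The double meaning is confined to score 1, higher scores still indicate useful visualization, and the introductory wording allows plain, fluorescing ducts a high score. The possible patient without a cystic duct, who is not excluded and for whom no code exists, is a side point; nothing shows that such patients would be common.

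**Conclusion.** The point holds as a flaw in a stated rule. The scale names one construct and anchors another, leaves the reference for improvement undefined, and lets score 1 stand for two opposite outcomes. The independent surgeon uses the same scale, so the second rating inherits the problem.

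The likely effect is to blur the dose comparison on this score and to add disagreement between raters and, in a multicenter trial, between centers. The size is unknown. In the illustrations, scoring 1 for 20% of patients (or of well-visualized patients, in the second model) costs between about 11 and 34 percentage points of power at 15 per arm: 100 − 89 = 11 for pair II, 69 − 39 = 30 for the second model, and 82 − 48 = 34 for pair I. The loss depends on the assumed distributions and on how often plain ducts are in fact scored 1.

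A reader might also infer that the trial's powered analysis is compromised. It is not: the duct-to-liver ratio is unaffected. The matter is still worth correcting, because this score is the only planned evidence on two of the three ducts in the hypothesis.

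**What to change.** Separate the two constructs on the scoring form.

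- At each reading, record for each of the three ducts whether it is identified under white light and whether it is identified under fluorescence (yes / no / not present). That is 3 × 2 = 6 tick boxes.
- Keep the 1–5 item for improvement over the white-light view only, with 1 meaning no improvement.
- In the SAP, report per-duct identification under fluorescence by arm as the secondary visualization outcome, and state which reading and rater it comes from.
- Have the blinded independent surgeon, who is already planned, use the same items on the recordings, so far as these show both views. If scoring in theatre is already complete, this is also the way to recover the per-duct information.

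The cost is a changed form, slightly longer scoring in theatre and a short addition to the SAP. No new reader or procedure is needed. Per-duct proportions will be imprecise at this size: even 15 of 15 gives an exact two-sided 95% lower limit of 0.025^(1/15) = 78%. They should be reported with intervals and not read as a powered comparison.

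### The primary outcome, the ImageJ bile duct-to-liver ratio, has no stated masking of the reader, no time point and no frame or region rule

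*Protocol*

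**What the plan says.** The SAP's power statement names the bile duct-to-liver fluorescence intensity ratio as the primary outcome, and its first sentence compares the assessments between doses by Mann-Whitney test. Protocol Section 6 (Research Plan) describes how the ratio is obtained: "A quantitative assessment will also be performed on the recorded visualization using ImageJ", dividing common bile duct signal by that of surrounding fat or liver. The SAP settles the denominator of the primary ratio as liver.

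Masking appears twice in Protocol Section 6. For the surgeon in the room: "The operating surgeon will be blinded to the dose given". For the video assessor: "The recorded visualization will also be assessed by a blinded independent surgeon who will use the same scale". The scale meant is the 1-5 qualitative score. The ImageJ sentence comes next and names neither a reader nor any masking. The Protocol then says of the ImageJ results: "These quantitative measurements will allow an independent measure of duct visualization".

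On video handling, Section 6 limits access to the study team and adds: "This will allow the team to perform the image analysis and related calculations". The one de-identification step is: "At the end of the study, the videos will be deidentified and maintained for possible future research".

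On timing, "At two points during the operation" introduces the primary surgeon's qualitative score. The first point is before dissection and the second is "upon completion of the dissection and establishment of the critical view of safety". No such statement is made for the ratio.

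**The concern.** ImageJ computes an intensity, but a person picks the moment in the recording, the frame and the regions. Those choices set both the numerator and the denominator of the ratio. If the person choosing knows the arm, the choices can lean one way without any intent, and the lean enters the primary comparison as if it were a dose effect. The plan states masking for the secondary, subjective score and leaves it unstated for the outcome on which the trial is powered.

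The Protocol presents the quantitative reading as an independent measure, yet states no safeguard that keeps it independent of the arm. A reader of the results could not rule out reader choice as a source of a difference. The masked 1-5 score is a partial cross-check, but it is a different measure and not the primary one.

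**Working it through.** **Step 1: what is stated for each assessment.**

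| Item | 1-5 score | ImageJ ratio (primary) |
|---|---|---|
| Who assesses | Operating surgeon; independent surgeon | Study team, person not identified |
| Masking | Stated for both | Not stated |
| Time point | Two points for the primary surgeon's score | Not stated |
| Structures | The three ducts | Common bile duct over liver (Protocol with SAP) |
| Frame and region rule | Not applicable | Not stated |

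The study coordinator is listed with the investigators (Protocol Section 2) and guides the dosing (Section 6), so at least one listed member of the study personnel knows the arm. The documents do not say that this person reads the images.

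**Step 2: the plan's own figures.** Inputs from both documents: difference 0.2, SD 0.15, alpha 0.05 (two-sided assumed). Standardized difference = 0.2/0.15 = 1.33. A two-sided t-test at 90% power needs 12.86, so 13 per arm, which reproduces the SAP's 26. At 15 per arm the t-test power is 94.1%, consistent with the Protocol's claim of more than 90%. Nothing below changes either sample size.

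**Step 3: illustration of an arm-dependent reading.** Assume no true difference, normally distributed ratios with SD 0.15, and a reading that shifts one arm by a constant. The test is the exact two-sided Mann-Whitney at 0.05. At 13 per arm it rejects for U ≤ 45 or U ≥ 124 (exact size 4.41%). At 15 per arm it rejects for U ≤ 64 or U ≥ 161 (exact size 4.53%). The shifts are assumptions; the rates for nonzero shifts are simulated.

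| Assumed shift | Share of the planned 0.2 | 13 per arm | 15 per arm |
|---|---|---|---|
| 0 | 0 | 4.4% | 4.5% |
| 0.02 | 0.02/0.2 = 10% | about 5.5% | about 6% |
| 0.05 | 0.05/0.2 = 25% | about 11% | about 13% |
| 0.10 | 0.10/0.2 = 50% | about 34% | about 39% |

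A small shift does little. A shift of a quarter of the planned difference more than doubles the error rate.

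**Step 4: illustration of an open time point.** Suppose the ratio were read at both intraoperative points and a result counted if either gave p < 0.05. This rule is assumed and is not in the plan. With no bias and no true difference, and a correlation between points from 0.9 down to 0, false positives are about 6.5% to 8.6% at 13 per arm and 6.7% to 8.8% at 15 per arm.

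**The case against.** The strongest reply is that silence is not evidence of an unmasked reading. Protocol Section 6 places knowledge of the dose with the anesthesiologist and the study coordinator, the reader is not identified, and no passage says the videos used for analysis carried the arm. That stands. A reader might infer from the end-of-study de-identification that the team analyzed videos labelled by arm. The documents do not support this: that step is tied to keeping videos for later research, and de-identification is a different thing from masking to dose.

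A reader might also infer that the ratio was planned at two points and that the plan failed to choose between them. The text does not support that either. The two points are given for the qualitative score only. The accurate statement is that the ratio has no stated time point, so Step 4 illustrates an assumed rule and is not a finding about this plan.

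Three further replies carry some weight.

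- Protocol Section 10.4 describes pilot and feasibility aspects and says that a primary efficacy difference is not being targeted. This tempers the severity. It does not remove the point, because the Protocol powers the trial on this ratio and the SAP names it primary and applies a 0.05 threshold.
- Brightness may hint at the dose whatever label the file carries, since 2.5/0.05 = 50. So coding alone may mask incompletely, which is why a fixed time point, frame and region rule is needed as well.
- The word independent might be read as a promise of masking. It describes the measurement and says nothing about who makes it.

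**Conclusion.** The point holds as a gap in the plan for the primary outcome: no stated masking of the ImageJ reader, no time point, and no frame or region rule. The missing masking is the main part, because the plan states it for the other assessors and it is cheap to add. The time point and image rules alone would be closer to missing detail.

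The size cannot be estimated from the documents. The illustration runs from almost no effect to a large one, depending entirely on the assumed shift. It also assumes normal ratios, a constant shift and equal arms. The documents do not show that the reader knew the arm or that any bias occurred, so the conclusion is that the plan should close the gap, not that the result is wrong.

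**What to change.** Before any ImageJ work, label the videos with study codes that do not reveal the arm, and have an existing team member without access to allocation make the readings. In the same step, write down one time point for the ratio, one rule for choosing frames, and one rule for placing and sizing regions, applied identically in both arms. Align the Protocol's fat-or-liver wording with the SAP's liver denominator; this is editorial.

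The SAP is in the past tense, so readings may already exist. In that case, re-read the retained videos masked under the written rule, report both sets, and say that the rule was set after the first readings. This depends on a surviving key that links each video to its arm. The Protocol keeps the videos in de-identified form and does not promise such a key; without one, a re-read cannot be analyzed by arm.

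The cost is some wording in both documents plus file-coding and reading time, with existing staff and recordings. At one time point this covers 2 × 13 = 26 to 2 × 15 = 30 patients. It is more if the SAP's 13 per arm applies to each center, which its closing sentence suggests; the number of centers is not given. Sample size, test and recruitment are unchanged. The remaining weakness is that masking may be incomplete because of brightness, and the report should say so.
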